#### 10.5.5. Reporting of SAEs

Reporting of an SAE to Pfizer Safety must be performed according to the processes described in Appendix 2 ([Section 10.2.4](#)).

#### 10.5.6. Reporting of SADEs

| SADE Reporting to Pfizer Safety                                                                                                                                                                                                                                                                                                                                                                                                                                                                                                                                                                                                                                                                                                                                                                                                                         |
|---------------------------------------------------------------------------------------------------------------------------------------------------------------------------------------------------------------------------------------------------------------------------------------------------------------------------------------------------------------------------------------------------------------------------------------------------------------------------------------------------------------------------------------------------------------------------------------------------------------------------------------------------------------------------------------------------------------------------------------------------------------------------------------------------------------------------------------------------------|
| 
Note: There are additional reporting obligations for medical device deficiencies that are potentially related to SAEs (ie, an SADE) that must fulfill the legal responsibility to notify appropriate regulatory authorities and other entities about certain safety information relating to medical devices being used in clinical studies.
 

• Any device deficiency that is associated with an SAE must be reported to the sponsor within 24 hours after the investigator determines that the event meets the definition of a device deficiency.

• The sponsor shall review all device deficiencies and determine and document in writing whether they could have led to an SAE. These shall be reported to the regulatory authorities and IRBs/ECs as required by national regulations.

 |

## 10.6. Appendix 6: Abbreviations

The following is a list of abbreviations that may be used in the protocol.

| Abbreviation      | Term                                                         |
|-------------------|--------------------------------------------------------------|
| 7vPnC             | 7-valent pneumococcal conjugate vaccine                      |
| 13vPnC            | 13-valent pneumococcal conjugate vaccine                     |
| 20vPnC            | 20-valent pneumococcal conjugate vaccine                     |
| ADE               | adverse device effect                                        |
| ADL               | activity/activities of daily living                          |
| AE                | adverse event                                                |
| AKI               | acute kidney injury                                          |
| AlPO 4 | aluminum phosphate                                           |
| ALT               | alanine aminotransferase                                     |
| AST               | aspartate aminotransferase                                   |
| AxMP              | auxiliary medicinal product                                  |
| BLQ               | below the limit of quantitation                              |
| C5a               | complement component 5a                                      |
| CBER              | Center for Biologics Evaluation and Research (United States) |
| CFR               | Code of Federal Regulations (United States)                  |
| CI                | confidence interval                                          |
| CIOMS             | Council for International Organizations of Medical Sciences  |
| CK                | creatinine kinase                                            |
| CKD-EPI           | Chronic Kidney Disease Epidemiology Collaboration            |
| CONSORT           | Consolidated Standards of Reporting Trials                   |
| COVID-19          | coronavirus disease 2019                                     |
| CRF               | case report form                                             |
| CCI               |                                                              |
| CRO               | contract research organization                               |
| CSR               | clinical study report                                        |
| CT                | clinical trial                                               |
| CTIS              | Clinical Trial Information System                            |
| DCT               | data collection tool                                         |
| DILI              | drug-induced liver injury                                    |
| DU                | dispensable unit                                             |
| EC                | ethics committee                                             |
| ECC               | emergency contact card                                       |
| ECG               | electrocardiogram                                            |
| eCrCl             | estimated creatinine clearance                               |
| eCRF              | electronic case report form                                  |
| EDB               | exposure during breastfeeding                                |
| e-diary           | electronic diary                                             |
| EDMC              | external data monitoring committee                           |

| Abbreviation | Term                                                                                                |
|--------------|-----------------------------------------------------------------------------------------------------|
| EDP          | exposure during pregnancy                                                                           |
| eGFR         | estimated glomerular filtration rate                                                                |
| EMA          | European Medicines Agency                                                                           |
| eSAE         | electronic serious adverse event                                                                    |
| EU           | European Union                                                                                      |
| EudraCT      | European Union Drug Regulating Authorities Clinical Trials (European Clinical Trials Database)      |
| FDA          | Food and Drug Administration (United States)                                                        |
| GCP          | Good Clinical Practice                                                                              |
| GGT          | gamma-glutamyl transferase                                                                          |
| GMC          | geometric mean concentration                                                                        |
| GMFR         | geometric mean fold rise                                                                            |
| GMT          | geometric mean titer                                                                                |
| HIPAA        | Health Insurance Portability and Accountability Act                                                 |
| HIV          | human immunodeficiency virus                                                                        |
| Ht           | height                                                                                              |
| IB           | investigator's brochure                                                                             |
| ICD          | informed consent document                                                                           |
| ICH          | International Council for Harmonisation of Technical Requirements for Pharmaceuticals for Human Use |
| ID           | identification                                                                                      |
| IgG          | immunoglobulin G                                                                                    |
| IMP          | investigational medicinal product                                                                   |
| IND          | investigational new drug                                                                            |
| INR          | international normalized ratio                                                                      |
| IP           | Internet Protocol                                                                                   |
| IPAL         | investigational product accountability log                                                          |
| IPD          | invasive pneumococcal disease                                                                       |
| IPM          | investigational product manual                                                                      |
| IRB          | institutional review board                                                                          |
| IRT          | interactive response technology                                                                     |
| ISF          | investigator site file                                                                              |
| ISO          | International Organization for Standardization                                                      |
| IWR          | interactive Web-based response                                                                      |
| KDIGO        | Kidney Disease: Improving Global Outcomes                                                           |
| LFT          | liver function test                                                                                 |
| LLOQ         | lower limit of quantitation                                                                         |
| MDR          | medical device regulation                                                                           |
| mITT         | modified intent-to-treat                                                                            |
| mPnC         | monovalent pneumococcal conjugate                                                                   |
| mPnC3        | monovalent pneumococcal serotype 3 conjugate                                                        |
| MQI          | medically qualified individual                                                                      |

| Abbreviation | Term                                                |
|--------------|-----------------------------------------------------|
| N/A          | not applicable                                      |
| NIMP         | noninvestigational medicinal product                |
| NIP          | national immunization program                       |
| OM           | otitis media                                        |
| OPA          | opsonophagocytic activity                           |
| PCV          | pneumococcal conjugate vaccine                      |
| PCV10        | 10-valent pneumococcal conjugate vaccine            |
| PCV15        | 15-valent pneumococcal conjugate vaccine            |
| PFS          | prefilled syringe                                   |
| PI           | principal investigator                              |
| PnC3         | pneumococcal serotype 3 conjugate                   |
| PPE          | personal protective equipment                       |
| PPSV23       | 23-valent pneumococcal polysaccharide vaccine       |
| PSSA         | Pfizer's Serious Adverse Event Submission Assistant |
| PT           | prothrombin time                                    |
| QTL          | quality tolerance limit                             |
| CCI          |                                                     |
| RCDC         | reverse cumulative distribution curve               |
| SADE         | serious adverse device effect                       |
| SAE          | serious adverse event                               |
| SAP          | statistical analysis plan                           |
| SARS-CoV-2   | severe acute respiratory syndrome coronavirus 2     |
| CCI          |                                                     |
| Screat       | serum creatinine                                    |
| Scys         | serum cystatin C                                    |
| SmPC         | summary of product characteristics                  |
| SoA          | schedule of activities                              |
| SOP          | standard operating procedure                        |
| SRSD         | single reference safety document                    |
| SUSAR        | suspected unexpected serious adverse reaction       |
| TBD          | to be determined                                    |
| T bili       | total bilirubin                                     |
| UADE         | unanticipated adverse device effect                 |
| ULN          | upper limit of normal                               |
| US           | United States                                       |
| USADE        | unanticipated serious adverse device effect         |
| VE           | vaccine efficacy                                    |

1. VERSION HISTORY

Table 1. Summary of Changes

Version/ Date	Associated Protocol Amendment	Rationale	Specific Changes
1 23 Oct 2023	Protocol amendment 1 15 Sep 2023	N/A	N/A
2 01 May 2024	Protocol amendment 1 15 Sep 2023	
Exploratory immunological assays may be performed after the final study results are generated.
 
Other minor updates were incorporated for clarity on the supplementary and sensitivity analyses and on the conduct of the study analyses.
	
Removed the analyses based on data from the exploratory immunological assays for the following exploratory endpoints (Sections 2.2, 3.3, and 6.3):
 
 • IgG and IgM subclass concentrations. • Relative dissociation rate of total serum antibodies measuring avidity of antibodies to antigen. • Serum IgG response to carrier protein. 
Added language to Section 3.1.1 to specify that related AEs that are considered local reactions be included in the reactogenicity reporting if the participant has e-diary data transmitted for at least 1 day.
 
In Section 4, clarified that the mITT population requires at least 1 dose of the study intervention.
 
Added language in Section 6.1.1.2 to include by-day reactogenicity graphs.
 
Added unplanned assessment data in Section 6.1.1.3.
 
Added language to Section 6.1.2.3 to include a sensitivity analysis for AEs leading to discontinuation.
 
Updated the language in Section 6.5.1.1 from “age at informed consent” to “age at Dose 1”.
 
Updated the ATC fourth-level classification to WHODD in Section 6.5.4.
 
Removed analysis of immunogenicity results through Visit 2 (1 month after Dose 1) in Section 7.2.1.

2. INTRODUCTION

This SAP provides detailed methodology for summary and statistical analyses of the data collected in Study C4801002.

2.1. Modifications to the Analysis Plan Described in the Protocol

The exploratory endpoints, estimands, and corresponding analyses are specified in the SAP.

2.2. Study Objectives, Endpoints, and Estimands

Type	Objectives	Endpoints	Estimands
	Primary Objectives:	Primary Endpoints:	Primary Estimands:
Safety	To describe the safety profile of the mPnC candidate administered as a 2-dose series in children ≥ 11 to ≤ 15 months of age	
 Prompted local reactions (redness, swelling, and pain at the injection site) Prompted systemic events (fever, decreased appetite, drowsiness/increased sleep, and irritability) AEs SAEs 	
In participants receiving at least 1 dose of the study intervention from each group, the percentage of participants reporting:
 
 Prompted local reactions within 7 days after each dose Prompted systemic events within 7 days after each dose AEs from Dose 1 through 1 month after Dose 2 SAEs from Dose 1 through 1 month after Dose 2
	Secondary Objectives:	Secondary Endpoints:	Secondary Estimands:
Immunogenicity	To describe the immune responses elicited by the mPnC candidate	
 IgG concentrations for the candidate serotype 	
In participants in compliance with the key protocol criteria (evaluable participants) from each group:
 
 Pneumococcal IgG GMCs 1 month after Dose 1 and 1 month after Dose 2 Percentages of participants with predefined IgG concentration 1 month after Dose 1 and 1 month after Dose 2 Pneumococcal IgG GMFRs from before Dose 1 to 1 month after Dose 1 and from 1 month after Dose 1 to 1 month after Dose 2
		
 OPA titers for the candidate serotype 	
In participants in compliance with the key protocol criteria (evaluable participants) from each group:
 
 Pneumococcal OPA GMTs 1 month after Dose 1 and 1 month after Dose 2 Pneumococcal OPA GMFRs from before Dose 1 to 1 month after Dose 1 and from 1 month after Dose 1 to 1 month after Dose 2

Type	Objectives	Endpoints	Estimands
	Exploratory Objectives:	Exploratory Endpoints:	Exploratory Estimands:
Immunogenicity	CCI		

The estimands corresponding to each primary and secondary objective are described in the table above. The estimands to evaluate each immunogenicity objective will be based on the evaluable immunogenicity population ([Section 4](#)). The estimands estimate the vaccine effect in the hypothetical setting where participants follow the study schedule and protocol requirements as directed.

2.3. Study Design

This is a Phase 2, multicenter, randomized, open-label study to describe the safety and immunogenicity of an mPnC candidate as a 2-dose series in healthy toddlers 11 through 15 months of age. This study will be conducted at investigator sites in the EU.

Approximately 100 children between 11 and 15 months of age who previously received the 2-dose PCV10 infant primary series as part of their routine vaccines will be enrolled.

Participants will be enrolled and randomized in a 1:1 ratio by site-based randomization to receive either the mPnC candidate or the control (mPnC control) as a 2-dose series at Visit 1 and Visit 3 (~2 months after Dose 1); participants will receive the same study intervention (either mPnC candidate or mPnC control) for both doses. Participants will be observed for 30 minutes after each dose. Participants will also receive their toddler (third) dose of PCV10 concomitantly at Visit 1.

3. ENDPOINTS AND BASELINE VARIABLES: DEFINITIONS AND CONVENTIONS

3.1. Primary Endpoints

- Local reactions (redness, swelling, and pain at the injection site) within 7 days after each dose.
- Systemic events (fever, decreased appetite, drowsiness/increased sleep, and irritability) within 7 days after each dose.

- AEs from Dose 1 through 1 month after Dose 2.
- SAEs from Dose 1 through 1 month after Dose 2.

3.1.1. Local Reactions and Systemic Events

The local reactions, including redness, swelling, and pain at the injection site, and the systemic events, including fever, decreased appetite, drowsiness/increased sleep, and irritability, are reported in the e-diary from Day 1 through Day 7 after each dose, where Day 1 is the day of study intervention administration at each dose. Besides the events collected in the e-diary, related AEs recorded on the AE CRF that are considered local reactions or any AEs (related or not) that are considered systemic events, starting within 7 days after study intervention will be included in the reactogenicity reporting if the participant has e-diary data transmitted for at least 1 day. This section describes derivations with details for the assessment of reactogenicity data: severity level, onset day, and duration.

Severity and Maximum Severity

The definitions for reactogenicity severity collected from the e-diary and from CRFs are described in [Appendix 2](#).

For each local reaction or systemic event, the maximum severity grade will be derived as follows:

Maximum severity grade = highest grade (maximum severity) within 7 days after each dose (Day 1 through Day 7) among severity grades reported for that local reaction or systemic event.

If a local reaction or systemic event is captured in more than 1 data source, eg, the e-diary, unplanned assessments, and/or the AE CRF, the highest grade across all sources will be used in the summary.

Onset Day

The onset day of each local reaction or systemic event will be derived. Onset day is defined as the first day of reporting the reaction or event with any severity after each dose.

Duration (First to Last Day Reported)

The duration (days) of each local reaction or systemic event will be calculated as the number of days from the start of the first reported reaction or event to the resolution of the last reported reaction or event, inclusive, after study intervention administration. For a reaction or event collected in the e-diary, the resolution is defined as the last day on which the reaction or event is recorded in the e-diary if the reaction or event lasted 7 days or less, or defined as the day on which the reaction or event ended beyond Day 7 (the latter will be collected on the CRF). For a reaction or event collected on the AE CRF, the AE end date will be considered the resolution date.

For a reaction or event collected in multiple sources, the earliest starting date and the latest end date will be used in calculating duration. If there is no known date when a reaction or event ends, the duration will be reported as unknown or missing.

If a reaction or event after Dose 1 is ongoing at the time of Dose 2, the Dose 2 date will be used as the end date for the duration calculation for that reaction or event.

Use of Antipyretic/Pain Medication

The use of antipyretic/pain medication is also recorded in the e-diary from Day 1 through Day 7, where Day 1 is the dosing day. For the use of antipyretic/pain medication from Day 1 through Day 7, the following endpoint and variable will be derived:

- Presence (yes or no) of use of antipyretic/pain medication after each dose.

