For determination of the evaluable immunogenicity populations, items 1 through 3 above will be computerized checks of the data, while item 4 will be determined by clinical review. A major protocol deviation is a protocol deviation that, in the opinion of the sponsor's clinician, would materially affect assessment of immunogenicity, eg, participant receipt of a prohibited vaccine or medication that might affect immune response or a medication error with suspected decrease in potency of the vaccine. The sponsor's clinician will identify those participants with major protocol deviations before any analysis specified in [Section 7.2.1](#) is performed.

Reactogenicity results (local reactions and systemic events) after a specified dose will be reported for all participants in the safety population who have any e-diary data collected after the specified dose.

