6. ANALYSES AND SUMMARIES

6.1. Primary Endpoints

6.1.1. Local Reactions and Systemic Events

6.1.1.1. Main Analysis

- Estimands:
 - The percentages of participants reporting local reactions (pain at the injection site, redness, and swelling) within 7 days after each dose ([Section 3.1.1](#)).
 - The percentages of participants reporting systemic events (fever, decreased appetite, drowsiness/increased sleep, and irritability) within 7 days after each dose ([Section 3.1.1](#)).
- Analysis set: Safety population with any e-diary data reported after each dose ([Section 4](#)).
- Analysis time point: Day 1 through Day 7 after each dose.
- Analysis methodology: Descriptive summary statistics ([Section 5.2.1](#)).
- Reporting results: The numerator (n) and denominator (N, defined as the number of participants who received the specific dose in the safety population and had any e-diary data reported after the specific dose) used for the calculation of the percentages. The percentages, and the associated 2-sided Clopper-Pearson 95% CI will be presented, by group and severity, for the following variable:
 - Maximum severity of each and any local reaction or systemic event on any day (Day 1 through Day 7) after each dose.

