6.1.2. Adverse Events

6.1.2.1. Main Analysis

- Estimand: The percentages of participants reporting AEs (excluding reactogenicity events collected on the AE CRF that are included in the local reaction or systemic event summary) from Dose 1 through 1 month after Dose 2 ([Section 3.1.2](#)).
- Analysis set: Safety population ([Section 4](#)).
- Analysis time point: Dose 1 through 1 month after Dose 2.
- Analysis methodology: Descriptive summary statistics ([Section 5.2.1](#)).
- Reporting results: The numerator (n) and the denominator (N) used in the percentage calculation, the percentage (%), and the corresponding 2-sided 95% Clopper-Pearson CI for participants reporting any AE, by system organ class and preferred term, will be presented for each group.

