Temperatures recorded in degrees Fahrenheit will be programmatically converted to degrees Celsius first for reporting. Fever will be grouped into ranges for the analysis according to Table 5. Maximum temperature range over the period from Day 1 through Day 7 will be mapped into the ranges described in Table 5 for summary of maximum temperature. If a fever was reported on the AE CRF within 7 days and no temperature was captured on the CRF or in the e-diary, the fever will be mapped to the ranges based on the AE intensity.

Table 5. Ranges for Fever

≥38.0°C to 38.4°C
>38.4°C to 38.9°C
>38.9°C to 40.0°C ^a
>40.0°C ^a

Note: Fever is defined as temperature ≥38.0°C based on e-diary data or indicated on the CRF within 7 days after administration.

a. Participants reporting a fever >104.0°F (>40.0°C) will be prompted to contact the study site.

If a local reaction or systemic event is captured in more than 1 data source, eg, the e-diary, unplanned assessments, and/or AE CRF, the highest grade will be used in the safety summary analysis.

Any reactogenicity events collected on the AE CRF from participants who do not have any e-diary data collected will be included in the AE/SAE summary as appropriate, not in the summary of local reactions or systemic events.

Document Approval Record

Document Name: C4801002 Statistical Analysis Plan Clean Copy, V2, 01 May 2024

Document Title: A PHASE 2, RANDOMIZED, OPEN-LABEL TRIAL TO DESCRIBE THE SAFETY AND IMMUNOGENICITY OF A MONOVALENT PNEUMOCOCCAL CONJUGATE CANDIDATE ADMINISTERED AS A 2-DOSE SERIES IN HEALTHY TODDLERS 11 THROUGH 15 MONTHS OF AGE WHO PREVIOUSLY RECEIVED THE PCV10 PRIMARY SERIES

Signed By:	Date(GMT)	Signing Capacity
PPD	01-May-2024 18:30:38	Final Approval

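### SAP 3.1.1 and Appendix 2 route CRF-recorded reactions by whether the child has any e-diary data at all, but the reactogenicity denominator is set per dose, so a post-Dose 2 reaction can be counted for a child who is not in N

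*SAP*

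**What the plan says.** Five places in the SAP bear on where a reaction recorded on the AE CRF is reported.

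- **3.1.1 (Local Reactions and Systemic Events).** Two kinds of CRF event with onset in the 7-day window are covered: related AEs that count as local reactions, and AEs of any causality that count as systemic events. Such an event "will be included in the reactogenicity reporting if the participant has e-diary data transmitted for at least 1 day". No dose is attached to that day of data.
- **Appendix 2 (Reactogenicity Data Consolidation).** Reactogenicity events on the AE CRF "from participants who do not have any e-diary data collected will be included in the AE/SAE summary as appropriate", and not in the local reaction or systemic event summary. Again no dose is named.
- **4 (Analysis Sets).** Reactogenicity results after a given dose cover the safety-population children "who have any e-diary data collected after the specified dose".
- **6.1.1.1 (Main Analysis).** N is the number of children who received the dose and "had any e-diary data reported after the specific dose".
- **6.1.2.1 (main AE analysis).** The AE percentages are computed "excluding reactogenicity events collected on the AE CRF that are included in the local reaction or systemic event summary".

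Protocol 9.3.2 consolidates related CRF events within 7 days after each dose and sets no diary condition, so it does not settle the question.

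**The concern.** The rule that admits an event works at participant level, while the denominator works at dose level. They disagree for a child who transmitted diary data after one dose but not the other.

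That child is foreseeable. Dose 2 is given 56 to 70 days after Visit 1, and protocol 8.10.3 allows for the diary application to be downloaded again or a device reissued. SAP 6.5.2.2 itself tabulates non-transmission after each dose. A child with no Dose 2 diary can still produce CRF events: reactions in the 30-minute observation are recorded as AEs, and AEs are asked about at Visit 4.

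Local reactions, systemic events and AEs are all primary endpoints, with about 50 children per group. Grade 4 reactions are collected only on the AE CRF, so where they appear depends on this rule.

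**Working it through.** **Tracing one child.** The child has diary data after Dose 1, none after Dose 2, and a qualifying reaction on the AE CRF within 7 days after Dose 2.

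1. *3.1.1 and Appendix 2 taken literally.* The child has at least one day of diary data (from Dose 1), so 3.1.1 admits the event to the reactogenicity summary. Appendix 2 does not redirect it, because the child has some diary data. The Dose 2 N in 6.1.1.1 leaves the child out. Since the event is now in the reactogenicity summary, 6.1.2.1 removes it from the main AE table. The numerator is no longer a subset of N, so the Clopper-Pearson interval does not describe a binomial proportion. In the extreme, 49 children with diaries all having the event plus this child gives 50/49 = 102%.
2. *Section 4 and the 6.1.1.1 analysis set govern.* The event is not in the reactogenicity summary, so the 6.1.2.1 exclusion does not apply. It stays in the main AE table over the full safety population.
3. *The two mixed in programming.* If the AE exclusion is coded from the 3.1.1 condition while the reactogenicity numerator is limited to the 6.1.1.1 N, the event appears in neither main table. This departs from the wording of 6.1.2.1.

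The same conflict arises with the doses reversed.

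**Size.** The plan's nearest figure is protocol Table 4: with 50 per group and a true rate of 5%, 1 − 0.95^50 = 0.923, matching the stated 92.3%. It supplies the group size but does not bear on routing.

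The documents give no rate of missing Dose 2 diaries. Assume 50 children per group receive Dose 2, m of them have no Dose 2 diary, and one of those m has a CRF reaction in a category with no other events. Then N = 50 − m. Exact 95% limits:

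- for 0/N, the upper limit is 1 − 0.025^(1/N);
- for 1/N, the lower limit is 1 − 0.975^(1/N), and the upper limit is the 97.5% point of Beta(2, N − 1).

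| m | N | Dose-specific rule | 3.1.1 read literally |
|---|---|---|---|
| 1 | 49 | 0/49 = 0% (0 to 7.3) | 1/49 = 2.0% (0.1 to 10.9) |
| 5 | 45 | 0/45 = 0% (0 to 7.9) | 1/45 = 2.2% (0.06 to 11.8) |
| 10 | 40 | 0/40 = 0% (0 to 8.8) | 1/40 = 2.5% (0.1 to 13.2) |

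Under the dose-specific rule the event is reported in the AE table instead, as 1/50 = 2.0% (0.1 to 10.6).

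**Where else the event would show under the literal reading.** SAP 6.1.2.3 repeats any AEs, immediate AEs and AEs leading to discontinuation using every AE CRF event, and the SAE table in 6.1.3 states no reactogenicity exclusion. The related-AE and severe-AE summaries in 6.1.2.2 carry the exclusion and have no such repeat. The reactogenicity sensitivity analysis in 6.1.1.3 uses only diary and unplanned-assessment data, so it omits events known only from the CRF.

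**The case against.** The best defence is that the sections can be read together. The sentence before the 3.1.1 condition describes diary reporting after each dose, and 6.5.2.2 measures transmission after each dose. The analysis set in 6.1.1.1 is the safety population with diary data after each dose, which should bind the numerator as well as N. If one day of data means a day in that dose's own window, 3.1.1, 4, 6.1.1.1 and 6.1.2.1 agree. This is a fair reading and probably the intended one, but it has to be supplied: the dose qualifier is present where N is defined and absent from both routing statements.

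A reader might go further and infer that the event is lost from both primary safety tables. The documents do not support that. SAP 6.1.2.1 takes out of the AE table only events that are actually in the reactogenicity summary. Appendix 2 says that events from children with no diary data go to the AE/SAE summary, but not that only those events may. Loss from both is a programming risk, not the written result.

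Nor would Grade 4 reactions disappear from view. The investigator must notify the sponsor of them immediately (protocol 8.3.3.1.1 and 8.3.3.1.2.1), they remain in the all-CRF repeat of any AEs, and serious ones are in the SAE table. These backstops are partial, since a Grade 4 reaction defined by an emergency room visit need not be an SAE.

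It also stands that sites review diary data frequently, which should keep wholly absent Dose 2 diaries few, and that the study is descriptive with no hypothesis test.

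**Conclusion.** The mismatch is real and minor. As written, 3.1.1 and Appendix 2 decide by participant what Sections 4 and 6.1.1.1 decide by dose. The literal result is a Dose 2 numerator that includes a child outside its denominator, with that event then dropped from the main AE table.

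Each such event shifts a Dose 2 category by about 2.0 to 2.5 percentage points, from 1/49 to 1/40. That range rests on the assumption that 1 to 10 of 50 children per group lack a Dose 2 diary. The documents give neither that number nor how often such a child would have a CRF reaction. The expected effect is small, and it matters mainly if the affected event is a rare severe one.

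**What to change.** In SAP 3.1.1, make the diary condition dose-specific by adding *after the specified dose* to the requirement for at least 1 day of transmitted data. In Appendix 2, add the same words to the description of participants with no e-diary data collected.

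Both statements then match Sections 4 and 6.1.1.1. A CRF reaction after a dose with no diary goes to the AE/SAE summary over the full safety-population N, and 6.1.2.1 needs no change. The cost is two phrases in the SAP and a matching programming specification, with no new data.
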